#### 3.5.3 Efficacy Population

The Efficacy population will consist of all subjects in the Safety population who received at least 1 dose of rVIII-SingleChain for either routine prophylaxis treatment or on-demand treatment during the study.

The Efficacy population might be the same as the Safety population. In this case, analyses will not be repeated for both the populations.

#### 3.5.4 Surgery Population

The Surgery population will include all subjects in the Safety population who received at least one dose of rVIII-SingleChain for surgical prophylaxis.

### 3.5.5 CCI

CCI

CCI

### 3.5.6 Subgroups/Subpopulations

The following subgroups will be defined:

- Age based on age in this study:
  - For PTPs (Arm 1 and Arm 3): 0 to < 6 years,  $\geq 6$  to < 12 years,  $\geq 12$  to < 18 years and  $\geq 18$  to  $\leq 65$  years, 0 to <12 years,  $\geq 12$  to  $\leq 65$  years;
- By Region (Europe, US, Rest of the world, Asia)
- Japan subgroup

Efficacy endpoint will be analyzed by

- Positive vs. negative test for non-inhibitory Anti-Drug Antibodies (ADAs) during the Study.

The incidence of inhibitors will be summarized by

- Race (White, Black, Asian, and Other)

Annualized Bleeding Rates will be presented by

- ADA status (Positive and Negative)

For PUPs analyses for Annualized Bleeding Rates, hemostatic efficacy, TEAE and IR will be presented by inhibitor status (Positive and Negative) at the time of assessment.

CCI

Analyses by inhibitor status or inhibitor group have been defined in this SAP within relevant sections, the definition of inhibitor status and inhibitor group are the following ones:

*Inhibitor positive*

A subject is inhibitor positive if he developed a titre value (from the central lab) of at least 0.6 BU/mL, and was also confirmed in the next assessment with a titre value of at least 0.6 BU/mL.

*Inhibitor negative*

[figure not shown]
A subject is inhibitor negative if his titre value (from the central lab) was below 0.6 BU/mL.

*Inhibitor eradicated*

It refers to a subject who was previously documented with a confirmed inhibitor positive titre result and at a later point in the study, his titre value decreased and became low enough to classify him as inhibitor negative (titre value < 0.6 BU/mL). However, in order to become inhibitor eradicated, an inhibitor positive subject must first present an initial inhibitor negative titre result which must be confirmed in the next assessment by another inhibitor negative titre result.

*Inhibitor status*

A subject's inhibitor status represents a period in the study in which he is either inhibitor positive (+) or inhibitor negative (-), depending on his titre value at a given time.

The above schema depicts a subject starting out as a negative inhibitor (-), which is the case for all subjects in the study. At some point in the study, i.e. at Time (c), his titre level went up and met the criteria for inhibitor positive status (+), which consisted of an initial titre value of  $\geq 0.6$  BU/mL, represented by (+) at Time (c), and was followed by a confirmatory titre value of  $\geq 0.6$  BU/mL in the next assessment, represented by (+)\* at Time (d). At Time (c), he is considered (+). When a subject becomes (+), the Investigator may administer an intensified prophylaxis (IP) treatment. Furthermore, he will be included in the CCI [REDACTED] to treat his inhibitory response to rVIII-SingleChain treatment. If the subject responds positively to IP and/or CCI [REDACTED], his titre values will improve (i.e. decrease) at later assessments. In the above schema, the subject became (-) at Time (e), which was followed by a confirmatory assessment (-)\* at Time (f) one month later. At Time (f), the subject is considered inhibitor eradicated.

From the above schema, we can state that:

Period of (+): Time reference after Time (c) up to Time (f), or Time (c) < Time reference  $\leq$  Time (f).

Period of (-): There will be two: on or before (+), and after (-)\*.

- On or before (+): Time (start) < Time reference  $\leq$  Time (c)
- After (-)\*: Time (f) < Time reference  $\leq$  Time (End)

By partitioning the study duration as periods of inhibitor status, analysis of time-dependent variables can be presented by inhibitor status.

*Inhibitor group*

An inhibitor group classifies a subject's inhibitor status overall during the study. Therefore, this classification is fixed for a subject, which differentiates itself from the classification by

inhibitor status for which a subject's inhibitor status may change from (-) to (+) over time according to his titre values.

The inhibitor positive group comprises of subjects who were confirmed (+) at any point during the study.

The inhibitor negative group comprises of subjects who were always (-) during the study.

For all subgroups defined in this section, in case of patients lower or equal than 3, the table will not be produced, data will only be provided in the listings.

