### AsBR

AsBR will be derived by inhibitor status and overall as follows:

$$(\text{number of bleeding events}) / (\text{observed treatment period of interest days}) * 365.25.$$

Only bleeding events requiring treatment will be included in the derivation of bleeding rates. The AsBR will be estimated for subjects who complete at least 8 weeks of treatment on the given inhibitor status using the subject's observed data. If the subject does not complete at least 8 weeks of treatment on the given inhibitor status, then the AsBR will be considered missing.

The number of spontaneous bleeding episodes per year based on a Poisson model and associated 95% CI and the number and percentage of subjects with zero bleeding episodes will be presented. In addition, the rate ratio of Prophylaxis modality to On-Demand modality (Prophylaxis- On-Demand) will be presented, along with the associated 95% CI, as obtained by the Poisson model.

Spontaneous bleeding episodes are those classified as 'Non-traumatic' in e-Diary or 'Spontaneous' in the eCRF. Annualized spontaneous bleeding rate will also be summarized for the following subgroup:

- Positive non-inhibitory Anti-Drug Antibodies (ADAs) and negative during the study
- Age based on age in this study: for PTPs: 0 to < 6 years,  $\geq 6$  to < 12 years,  $\geq 12$  to < 18 years and  $\geq 18$  to  $\leq 65$  years, 0 to <12 years,  $\geq 12$  to  $\leq 65$  years.
- Prophylaxis frequency: every second day, 3 times per week, 2 times per week, other regimen.

In these subgroup analyses rate ratio of Prophylaxis modality to On-Demand modality won't be displayed.

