**4.7.4.1 Non-inhibitory Anti-Drug Antibodies (ADAs)**

Non-inhibitory anti-drug antibodies (ADAs) screening test results and the confirmatory ADAs IgG and ADAs IgM test results will be tabulated by scheduled visit and inhibitor group. The percentages (positive or negative) at each visit will be based on the number of subjects who were tested at the visit. The final result will be positive if one of the confirmatory tests is positive; otherwise the final result will be negative. The final result over all visits will be based on the final assessment at EOS.

In addition, a shift analysis showing the change in status between baseline and anytime during the study, as well as between baseline and final assessment (EOS) will be provided.

The following information will be summarized, displaying the number and percentage of subjects:

- Positive anytime during the study
- Positive at baseline
- Positive at baseline and anytime after baseline
- Positive at baseline and at the end-of-study visit
- Negative at baseline and positive anytime post-baseline
- Negative at baseline and positive at the End-of-study Visit.

Baseline is the baseline visit of the current study.

Anti-rVIII antibody test results will be summarized for the Safety population overall and by age.

The relationship between ADA and inhibitor titer will be explored graphically overall and by subject displaying in a scatter plot inhibitor titer values along visits stratifying by ADA status.

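### Bleeding rates by ADA status use one whole-study label per subject, so in converters a later sample classifies earlier bleeds and time; the contrast is distorted, in a direction that depends on how ADA onset relates to bleeding

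*SAP*

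**What the plan says.** SAP 3.5.6 lists, for the efficacy endpoint, a subgroup of "Positive vs. negative test for non-inhibitory Anti-Drug Antibodies (ADAs) during the Study", and for annualized bleeding rates a subgroup of "ADA status (Positive and Negative". The AsBR part of SAP 4.6.1.1 repeats the label: "Positive non-inhibitory Anti-Drug Antibodies (ADAs) and negative during the study". AsBR is a primary efficacy endpoint in PUPs. SAP 4.6 runs the efficacy evaluation period from treatment Day 1 to the later of the End of Study Visit and the last dose. No ADA onset date, ADA-positive period or split of follow-up by ADA is defined.

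Inhibitors are handled differently. In PUPs, bleeding rates "will be presented by inhibitor status (Positive and Negative) at the time of assessment", and SAP 3.5.6 explains the method: "By partitioning the study duration as periods of inhibitor status, analysis of time-dependent variables can be presented by inhibitor status".

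SAP 4.7.4.1, which covers ADA test results, counts "Positive anytime during the study" and, as a separate category, "Negative at baseline and positive anytime post-baseline". It also says "The final result over all visits will be based on the final assessment at EOS". The bleeding-rate sections refer to neither definition.

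**The concern.** ADA status can change during follow-up, and the plan expects this, since it has a category for subjects who convert after baseline. With one label per subject and the whole efficacy period as denominator, a converter's bleeds and time before the first positive sample count as ADA-positive experience. The future classifies the past.

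The SAP avoids this for inhibitor status, so the omission for ADA is a gap in a method it already has. The ADA subgroup is the planned comparison of bleeding by non-inhibitory antibody status. A near-null ratio could be read as reassurance that these antibodies do not weaken protection, and a raised ratio as a sign that they do. Either could come from the labelling. PUPs matter most here: they enter without prior FVIII product (short-term blood products excepted), so conversion on study is plausible, and AsBR is primary for them.

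**Working it through.** The documents give no figure for the ADA comparison, so there is none to reproduce. The rate ratios, time shares and simulation settings below are assumptions.

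**1. Fixed label, equal background rates.** Let RR be the true rate ratio after ADA onset and f the share of the ADA-positive group's follow-up that precedes onset. Read the label as positive at any time. Relative to ADA-negative subjects, the observed ratio is

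observed = f × 1 + (1 − f) × RR

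| True RR | f = 0.10 | f = 0.33 | f = 0.50 | f = 0.75 |
|---|---|---|---|---|
| 1.5 | 1.45 | 1.33 | 1.25 | 1.12 |
| 2 | 1.90 | 1.67 | 1.50 | 1.25 |
| 3 | 2.80 | 2.33 | 2.00 | 1.50 |

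For RR = 2 and f = 1/3: 0.333 + 0.667 × 2 = 1.67. This f corresponds to a PUP first positive at 25 EDs who leaves at 75 EDs, if EDs accrue evenly (25/75 = 0.33). Protocol 8.10.2 ends monthly prophylaxis visits at 25 EDs, and Protocol 8.10.6 ends the study at 75 EDs for inhibitor-negative PUPs. Subjects positive at baseline have f = 0 and lower the group's average f.

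**2. Unequal background rates.** If future converters already bleed at k times the rate of the others,

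observed = k × [f + (1 − f) × RR]

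With f = 0.50:
- k = 1.5, RR = 1: 1.5 × 1.00 = 1.50, a false signal.
- k = 1.5, RR = 1.5: 1.5 × 1.25 = 1.88, inflated.
- k = 0.7, RR = 2: 0.7 × 1.50 = 1.05, almost hidden.

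**3. Why k may exceed 1 in on-demand PUPs.** Protocol 8.10.2 sets their follow-up visits one month after each dose, and Protocol 8.6.1 takes ADA samples at every scheduled PUP visit. More bleeds mean more doses, more exposure and more tests.

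**4. Simulation.** Poisson bleeds in 200,000 subjects, mean 6 per year, 2 years of follow-up. Onset was either unrelated to bleeding or had a 3% chance per treated bleed. Variation between subjects, where present, was gamma with shape 2.

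| Onset | True RR | Fixed label | Split at onset |
|---|---|---|---|
| Unrelated to bleeding (f = 0.47) | 1.5 | 1.27 | 1.50 |
| Unrelated to bleeding (f = 0.47) | 2 | 1.53 | 2.00 |
| Bleed-driven, rates vary (f = 0.46) | 1 | 1.77 | 1.55 |
| Bleed-driven, rates vary (f = 0.46) | 1.5 | 2.24 | 2.31 |
| Bleed-driven, rates vary (f = 0.46) | 2 | 2.71 | 3.09 |

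The first two rows are the same with and without shape-2 variation. With bleed-driven onset but no variation between subjects, the split recovers 1.00, 1.50 and 2.00, while the fixed label gives 1.10, 1.37 and 1.65. The split therefore removes the error from misplaced time. It does not remove the selection of heavy bleeders into the ADA-positive group.

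**The case against.** Several points on the other side stand.

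- **Direction.** A reader might infer that any ADA effect is always diluted. The documents do not support that: dose-triggered visits in on-demand PUPs can push the ratio the other way.
- **The remedy is partial.** With bleed-driven onset and varying rates, the split was slightly further from the truth than the fixed label at true ratios of 1.5 and 2 (2.31 against 2.24, and 3.09 against 2.71). It belongs beside the fixed-label table, not in its place.
- **A minimum period can backfire.** The 8-week rules in SAP 4.6.1.1 and 4.6.2.1 apply to inhibitor status and regimen. Carried over to ADA periods, such a rule would drop late converters, the subjects most affected.
- **Reach.** The SAP records the PTP report as completed in November 2019 and, in 4.1.2, the PTP analysis as complete. PTP samples follow the 10, 50 and 100 ED milestones, so longer follow-up does not by itself add scheduled tests, and onset is known only between widely spaced samples.
- **Weight.** The tables are descriptive, Protocol 11.3 plans no p values, and SAP 3.5.6 suppresses subgroup tables at 3 or fewer subjects. Neutralising antibodies have their own time-split analyses.

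A reader might also infer that the End of Study result in SAP 4.7.4.1 competes with the label in the bleeding tables and must be deleted. No section assigns it to those tables. It belongs to the tabulation of ADA results and can stay there. What is missing is a statement of which definition the bleeding tables use.

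These points narrow the claim. They do not change the fact that pre-conversion bleeds and time are counted as ADA-positive.

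**Conclusion.** The point holds in limited form. For subjects who convert after baseline, the bleeding tables by ADA status let a later sample classify earlier bleeds and time, although the same SAP section shows how to avoid this for inhibitors.

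With an ever-positive label, equal pre-onset rates and onset unrelated to bleeding, a true ratio of 2 shrinks to between 1.67 and 1.25 as the pre-onset share rises from 33% to 75%. If bleeding drives exposure and testing, the contrast can be inflated instead, to 1.77 for a true ratio of 1 in one assumed setting. The actual size cannot be known in advance, because the documents give neither the number of converters nor the timing of conversion.

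This should be corrected before the PUP tables are produced. It bears on a descriptive subgroup comparison, not on the overall AsBR or the inhibitor endpoints.

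**What to change.** For the PUP tables still to be produced, amend SAP 3.5.6 and 4.6.1.1 as follows.

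1. State that the fixed label means a positive confirmatory ADA test at any time during the study.
2. Beside the fixed-label table, add an analysis that assigns bleeds and person-time before the first such sample to ADA-negative and those after it to ADA-positive.
3. Count baseline positives as positive from Day 1 and show them separately.
4. Present results within regimen (prophylaxis, on-demand).
5. State how a return to ADA-negative is handled; SAP 3.5.6 already has such a rule for inhibitors.
6. Estimate rates from pooled events over person-time, using a Poisson model with a log-time offset as SAP 4.13 already codes, so that an 8-week minimum does not remove late converters.
7. Add a note that the split does not remove bias from bleed-driven sampling, so the on-demand results need particular caution.

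The cost is SAP wording and one derived time-varying flag built on the existing inhibitor logic. The onset date is approximate, since conversion is known only to lie between two samples. With at least 24 PUPs planned under Protocol 3.5, the groups will be small, and some tables may be suppressed under the rule of 3 or fewer subjects, leaving listings only.

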3.3 Planned Study Duration

The duration of the study for an individual subject is expected to be approximately 6 years to achieve the following number of EDs with rVIII-SingleChain:

- PTPs in Arm 1 may enroll immediately after participation in previous rVIII-SingleChain studies and continue treatment until achieving at least 100 EDs (including EDs from any previous rVIII-SingleChain study).

- Inhibitor-negative PUPs in Arm 2 will receive treatment in this study until they achieve 75 EDs with rVIII-SingleChain; the overall study duration is expected to be up to 6 years. Additional time of up to 3 years in the study may occur for PUPs that develop an inhibitor:
 - CCI [REDACTED]
 - For inhibitor-positive PUPs who remain in the **main study** who have achieved eradication, the End of Study Visit will occur when they complete the 12-month post eradication follow-up period in the main study. The maximum duration of the inhibitor treatment period is 24 months starting when the dose is initially adjusted to treat the inhibitor, and if no dose adjustment is performed to treat the inhibitor then the duration of inhibitor treatment will be from the date of inhibitor diagnosis.
- PTPs in Arm 3 will receive treatment in this study until they achieve at least 100 EDs with rVIII-SingleChain (excluding EDs from any previous rVIII-SingleChain study that the subject may have participated in).

In all study arms, subjects will complete the study as outlined in [Section 3.1](#) or until the study is terminated by the sponsor.

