## 4.5 Exposure

### 4.5.1 Exposure Days and Time on Study

Exposure days (EDs) and time on study will be summarized for the Safety, Efficacy, Surgery and CCI population. Exposure for subjects coming from the pivotal studies (1001, 3002) will also be assessed cumulatively.

An ED is defined as any day that the subject receives an injection of rVIII-SingleChain regardless of the number of injections on that day. Total EDs are cumulative from previous pivotal study for PTPs in Arm 1 and are calculated from the first dose of rVIII-SingleChain, including all EDs to rVIII-SingleChain from any study or the surgical component of this study.

CCI

The number of EDs will be summarized as both a continuous and categorical variable by age group as defined in this section.

The following categories will be presented, based on first day of dosing in the pivotal study for Arm 1 and in this study for Arm 2 and Arm 3:

- PTPs: 0-10 EDs, >10-15 EDs, >15-50 EDs, >50-75 EDs, >75-100 EDs, >100 EDs
- PUPs: 0-10 EDs, >10-25 EDs, >25-50 EDs, > 50 EDs

Exposure days in the current study will be summarized as well, as both a continuous and categorical variable as described above. EDs in the current study are counted from first dose in this study or the surgical component of this study or the CCI [REDACTED]

Total time on study (days) will be derived as:

$[Maximum \text{ (rVIII-SingleChain last dose date, End of study visit date)}] - [Minimum \text{ (rVIII-SingleChain first dose date considering pivotal study for PTPs Arm 1, Day 1 date in the current study)}] + 1.$

Time on current study (days) will be derived as:

$[Maximum \text{ (rVIII-SingleChain last dose date, End of study visit date)}] - [Minimum \text{ (rVIII-SingleChain first dose date during the current study, Day 1 date in the current study)}] + 1.$

Total time on study and time on current study in days, weeks (days/7), and months (days/30.4375) will be summarized using descriptive statistics. Time on study will be described with statistics for continuous variables. Total subject-years will be provided.

CCI [REDACTED]

ED will also be summarized by Inhibitor Level (high/low titer) on PUPs.

In addition, a separate exposure analysis over the period of inhibitor development will be provided while subjects are inhibitor positive on PUPs.

CCI [REDACTED]

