#### 4.7.2 Adverse Events

An AE is any untoward medical occurrence in a subject or clinical investigation subject administered a pharmaceutical product and which does not necessarily have a causal relationship with this treatment.

Adverse events will be coded and grouped by SOC and PT using the MedDRA Version 16.1 or higher.

An AE will be regarded as treatment-emergent (TEAE) if it was present prior to the first dose of rVIII-SingleChain and subsequently worsened in severity, or was not present prior to the first dose but subsequently appeared. For this determination, partially missing dates will be handled as outlined in [4.12.1](#). An AE will be assumed to be treatment-emergent if non-treatment emergence cannot be reasonably ruled out. All AEs reported for PTP in Arm 1 will be considered treatment-emergent.

TEAEs will include AEs that occurred during the surgical period, but will exclude TEAEs during the CCI period. A summary table with all the TEAEs that occurred during the study will be also provided.

Summary of AEs while subjects are inhibitor positive should be performed. All AEs while subjects are inhibitor positive will be listed. Serious AEs while subjects are inhibitor positive will also be listed.

An overview summary table of COVID-19 associated treatment-emergent adverse events (TEAEs), including number and percentages of subjects as well as the number of events, will be provided if the number of Covid-19 associated TEAE is at least equal to 10. Otherwise, Covid-19 associated TEAEs will only be listed.

TEAEs with missing causality assessment will be considered as related.

TEAEs leading to withdrawal are all TEAEs reported on the AE log with “Was subject terminated from study due to the AE” as “Yes” or “Action taken with study drug” with response of “Permanently discontinued”.

The following will be summarized by SOC and PT; displaying the number and percentage of subjects who experience at least 1 event, as well as the total number of events:

- All AEs. This will include TEAEs, and AEs that are not treatment emergent.
- All SAEs. This will include TE SAEs, and SAEs that are not treatment-emergent.
- TEAEs
- Related TEAEs
- Non-serious TEAEs
- Non-serious TEAE by frequency threshold of preferred term (>1%, >2%, >3%, >4%, and >5% in either age cohort)
- TE SAEs

- Related TE SAEs
- TEAEs by maximum severity. If a subject experiences multiple events that map to a single PT, the only the most severe event will be counted.

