- Covid-19 TEAEs (considering the same rule of 10 AEs described for the summary table)
- TEAEs while subjects are inhibitor positive

In addition, the SOCs and PTs will be displayed in decreasing frequency. These displays will include the number of subjects who experience at least 1 event, as well as the total number of events.

TEAEs and TE SAEs will be summarized for the Safety population. TEAEs starting during the surgical period will be summarized by SOCs and PTs for the Surgery population. TEAEs starting during the **CCI** period will be summarized overall and by SOCs and PTs for the **CCI** population.

All AEs (including all SAEs) will be presented in the individual subject listings. SAEs, deaths, and discontinuations due to AEs will be supported by separate listings.

AEs occurring within one month prior to positive inhibitor development will be listed.

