- The minimum and maximum values will be presented with the same number of decimal places as the raw data collected. The mean and percentiles (e.g. median, Q1, and Q3) will be presented using one additional decimal place. The standard deviation and standard error will be presented using two additional decimal places. PK parameters should have a minimum of 3 significant figures.
- Percentages will be presented to 1 significant decimal place in general. The denominator will be the total size of the sample, N, unless otherwise noted.

- Any p-values reported on default output from statistical software may be reported at the default level of precision, with one exception: p-values of 0.0000 or 10E-4 or below will be reported as <0.0001.
- The *left and right margins* of all tables and listings will be a minimum of 2.1 cm from the left and 1.9cm from the right. The *top and bottom margins* will be a minimum 2.92cm. *Header and footer* will be both 1.27 cm.

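### Adverse events in PUPs are tabulated by inhibitor status as subject percentages and event counts, with no time at risk and no stated denominator for each status, although follow-up in the two states is unequal

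*SAP*

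**What the plan says.** - **Status varies over time.** SAP 3.5.6 plans that "TEAE and IR will be presented by inhibitor status (Positive and Negative) at the time of assessment" and divides each boy's follow-up into periods. Positive time runs from the first positive titre, once confirmed, to the titre that confirms eradication. For negative time the SAP says "Period of (-): There will be two: on or before (+), and after" confirmed eradication.
- **Display.** SAP 4.7.2 summarises events by system organ class and preferred term, "displaying the number and percentage of subjects who experience at least 1 event, as well as the total number of events". Its list includes "TEAEs while subjects are inhibitor positive". SAP 4.7.2.2 uses the same display for medical events of special interest, by inhibitor status and overall.
- **Denominator.** SAP 5.1 sets a general rule: "The denominator will be the total size of the sample, N, unless otherwise noted". No other denominator is noted for adverse events by status.
- **Exposure.** In SAP 4.5.1, "Total subject-years will be provided", without a split by inhibitor status. A separate exposure analysis is planned for the inhibitor-positive period. Neither is linked to the adverse event tables.
- **Length of stay.** Protocol 3.3: "Inhibitor-negative PUPs in Arm 2 will receive treatment in this study until they achieve 75 EDs with rVIII-SingleChain". For boys with an inhibitor who stay in the main study, inhibitor treatment lasts at most 24 months, and follow-up after eradication is 12 months.

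**The concern.** A percentage with at least 1 event rises with the time observed, and so does a count of events. When the same boys move between two states and spend different lengths of time in each, neither figure separates how often events happen from how long the boys were watched.

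The SAP recognises this for bleeding. In 4.6.1.1 the annualized spontaneous bleeding rate by inhibitor status is divided by observed days and set to missing below 8 weeks in that status. SAP 4.11 explains the 8-week rule as avoiding bias from short evaluation periods. Adverse events over the same periods get no equivalent treatment.

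These tables are where a reader will look to learn whether boys with an inhibitor have more adverse events. An apparent excess, or its absence, could come from follow-up length alone. If the denominator is left unstated, a reader also cannot tell whether a percentage refers to the boys who were ever positive or to all PUPs.

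**Working it through.** **Plan's own figure.** Protocol 3.3 gives up to 3 years of additional time for boys with an inhibitor. This reproduces: 24 months of treatment + 12 months of follow-up = 36 months. The documents state no figure for time at risk or event rate by status.

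**Inputs**
- 75 EDs; 24-month cap; 12 months after eradication; study duration up to 6 years (Protocol 3.3).
- 2 to 3 injections per week. Protocol 3.2.1 reports this for earlier studies. Arm 2 schedules are at the investigator's discretion, so it is an assumption here.
- Short positive period for illustration: 56 days, the 8-week minimum used for bleeding rates.
- Event rate: assumed, equal in both states, varied from 0.25 to 4 per year.

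**Time in state**
- 75 / 2 = 37.5 weeks (0.72 year); 75 / 3 = 25 weeks (0.48 year).
- 24 months against these: 2.8 and 4.2 times as long.
- An on-demand boy followed for up to 6 years while negative, against 24 months positive: 6 / 2 = 3-fold the other way.

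**Chance of at least 1 event** = 1 - exp(-rate x years), in percent:

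| Rate per year, same in both states | 56 days | 75 EDs, 3 per week | 75 EDs, 2 per week | 6 months | 24 months | 6 years |
|---|---|---|---|---|---|---|
| 0.25 | 3.8 | 11.3 | 16.4 | 11.8 | 39.3 | 77.7 |
| 1 | 14.2 | 38.1 | 51.3 | 39.3 | 86.5 | 99.8 |
| 4 | 45.8 | 85.3 | 94.4 | 86.5 | 100.0 | 100.0 |

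For example, 1 - exp(-1 x 2) = 86.5% and 1 - exp(-1 x 0.48) = 38%. In every cell the events per subject-year are equal by construction, so a rate would show a ratio of 1.

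**Whole arm.** Take 24 PUPs, of whom 35.4% become positive after 12 EDs (background figures in Protocol 1.1, used as assumptions), all on prophylaxis at 2-3 per week. Mean negative time per boy without post-eradication follow-up:
- 2 per week: 0.646 x 0.72 + 0.354 x 0.115 = 0.50 year
- 3 per week: 0.646 x 0.48 + 0.354 x 0.077 = 0.34 year

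Adding 12 months after eradication for each positive boy adds 0.354 year, giving 0.86 and 0.69.

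| Positive period | Positive / negative mean time |
|---|---|
| 24 months, no post-eradication time | 4.0-5.9 |
| 24 months, with 12 months after eradication | 2.3-2.9 |
| 6 months, with or without the 12 months | 0.6-1.5 |
| 56 days, with or without the 12 months | 0.2-0.5 |

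The ratio can be several-fold in either direction, or near 1.

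**Denominator, illustrative counts only.** If 8 of 24 boys were ever positive and 6 of them had an event while positive, the percentage is 6/8 = 75% of those at risk, but 6/24 = 25% if the general rule in SAP 5.1 were applied.

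**The case against.** Several points on the other side are sound, and they limit the concern.

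- **Percentages are not the only display.** Event counts are shown too, exposure while positive is analysed separately, and events while positive are listed. A crude rate for the positive period might be worked out by hand. But negative time is not explicitly planned by status. SAP 4.7.2 also excludes a redacted period from the TEAEs, so a hand-made rate could pair a numerator and a denominator covering different time.
- **The design does not fix the times.** A reader might infer that positive time is several times longer by design. The documents do not support that: 75 EDs is a target and 24 months is a cap. The 12 months after eradication count as negative time, and on-demand boys may need far longer to reach 75 EDs. How much positive time reaches these tables is also hidden by the redaction.
- **The whole-sample denominator is only a default.** A reader might infer that boys who were never positive will be counted in the positive column. SAP 5.1 allows exceptions, and the table shells are in a separate document not seen here. The gap is that no denominator is stated, although SAP 4.7.4.1 and 4.7.4.2 do state one for antibody results.
- **The tables are descriptive.** Protocol 11.3 plans no p-values, and the table of events while positive names no comparator. SAP 3.5.6 also suppresses subgroup tables with 3 or fewer patients. At the 35.4% background figure about 8 of 24 boys would be positive (0.354 x 24 = 8.5), so the tables would probably be produced.

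**Conclusion.** The concern holds as a reporting gap. Adverse events in PUPs by inhibitor status are planned as subject percentages and event counts, without time at risk and without a stated denominator for each status. With identical underlying rates, the percentages can differ widely: at 1 event per year, 14% over 56 days against 86.5% over 24 months, with 38-51% for 75 EDs on prophylaxis in between. Neither direction nor size can be predicted from the plan, so a reader cannot correct for it by eye.

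The figures rest on a constant event rate, on dosing 2-3 times weekly carried over from earlier studies, and on 24 months taken as 2 calendar years. The arm-level ratios also rest on background inhibitor figures that may not apply to this arm. The documents do not support saying that the positive column must show an excess, or that the denominator will be all PUPs. The point is minor: the tables are descriptive and no primary endpoint depends on them.

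**What to change.** Add to SAP 4.7.2 and 4.7.2.2, for every PUP table by or within inhibitor status:

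1. The denominator is the number of boys with any time in that status.
2. Each table shows subject-years in that status and events per subject-year with a 95% CI. The interval is descriptive, either exact Poisson or one that allows for repeated events in the same boy.
3. Person-time follows the status periods of SAP 3.5.6 and leaves out the same redacted period that is excluded from the TEAE count.

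**Cost.** A short SAP addition and extra columns in the tables. Subject-years by status are not yet planned in SAP 4.5.1 and must be derived, but the bleeding-rate analysis by status already needs observed treatment days per boy in each status. The rates will be imprecise. Under the arm-level assumptions above, total positive time is 4.2 subject-years if each positive period lasts 6 months and 17.0 if each lasts 24 months (24 x 0.354 x 0.5 and 24 x 0.354 x 2). The intervals will make that imprecision visible.
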